5.2 Planned Duration of Study

Full screening may take 28 days after completion of phone screening. The Preparatory Period begins at enrollment and can be as brief as 7 days, but depending on medication tapering could be as long as 56 days to ensure an appropriate medication washout of at least five half-lives of pre-study psychiatric medications and active metabolites, and at least 7 days for stabilization prior to the Baseline CAPS-5 T1 (Visit 3).

Enrollment Confirmation takes place at the completion of the Preparatory Period, at which time the Treatment period will commence. The approximately 12-week Treatment Period will consist of three Experimental Sessions 3 to 5 weeks apart with associated non-drug Integrative Sessions and CAPS-5 assessments.

After the final Integrative Session 3.3 (Visit 18), participants will enter follow-up with no planned study visits for approximately 4 weeks, after which the Primary Outcome CAPS-5 T4 assessment will take place. Although there are allowable windows for all visits throughout the protocol, the overall timelines should comply with the target timing of the Primary Outcome CAPS-5 T4 assessment, which must be completed 18 weeks (± 3 weeks) (105 to 147 days) post Baseline, even if the maximum possible visit windows were used between visits. Other visits should be scheduled to ensure the timing of the Primary Outcome CAPS-5 T4 assessment is appropriate. The Study Termination visit follows 1 to 9 days after the final CAPS-5 assessment.

The minimum time that a participant who completes all study visits from Screening to Study Termination will be in the clinical trial is 19 weeks, and the maximum is 38 weeks. The average participant is expected to complete the study in 27 weeks. Any delays between visits outside of the protocol-defined windows may result in a corresponding extension of study duration and should be documented as a deviation as appropriate.

All participants who complete the study will be asked to participate in a LTFU extension study with one visit 12 months after the last Experimental Session. Upon unblinding after database lock, all participants who were assigned to placebo (regardless of CAPS-5 scores), completed the study, meet criteria, and are in good standing with the clinical site will be offered the opportunity to enroll in an open-label safety study of manualized MDMA-assisted psychotherapy. This open-label safety study will take place at least 18 months after the first participant is enrolled in MAPP1 and will last 19 to 38 weeks, and will follow a design similar to this protocol.

5.2.1 Interruptions and Accommodations Due to COVID-19 Pandemic or Any Other Unforeseen Emergency at Clinic Locations

This clinical trial has been interrupted by the Coronavirus Disease 2019 (COVID-19) global pandemic. Accommodations may be required for study continuation and participant and study site

staff safety due to this emergency or any other unforeseen emergency in the future. The following accommodations in the protocol will be allowed, captured and noted in the Clinical Study Report as COVID-19 deviations:

- Integrative Sessions may be conducted by telemedicine
- Delaying the start of medication tapering after enrollment and the subsequent Treatment Period per [Section 12.1 Tapering Instructions](#)
- Delaying Experimental Sessions and associated Integrative Sessions
- Delaying Independent Rater assessments for participants who cannot complete them remotely off-site
- Use of prohibited medications and/or cannabis or initiation of new psychotherapy for participants with significant study delays, which will be reviewed by the study team before each Experimental Session and re-tapered prior to resuming treatment per [Section 12.0 Concomitant Medications](#).

For any participant with COVID-19 related illness, continued trial participation after full recovery of the disease may be appropriate after discussion between the site physicians and Medical Monitors on a case-by-case basis.

5.3 Discontinuation and Completion Criteria

5.3.1 Complete or Evaluable Participants

Participants who are considered complete or evaluable will be defined as follows:

- A participant is considered ‘Evaluable’ and eligible for the mITT analysis if they have completed at least one Experimental Session and one CAPS-5 assessment beyond Baseline.
- A participant is considered ‘Evaluable and Completed Per Protocol’ if they have completed all Experimental Sessions and CAPS-5 assessments as planned. These participants will be included in the mITT analysis set and the Per Protocol analysis set.
- A participant is considered ‘Evaluable and Early Termination’ if they have completed at least one Experimental Session and one CAPS-5 assessment beyond Baseline but terminated early. These participants will be included in the mITT analysis.
- A participant is considered to be in good standing with the clinical site if, in the opinion of the investigator and/or therapy team, the participant was compliant with protocol requirements, even if they were unable to complete all study visits.

5.3.2 Screen Failures

‘Screen Failures’ are defined as participants who pass phone screening but are deemed ineligible before successfully enrolling in the study at Visit 0. Screen failures may fail to meet all Inclusion Criteria and may meet one or more Exclusion Criteria or withdraw consent prior to Enrollment. All potential participants who begin Screening will be tracked on a Screening Log, and reasons for Screen Failure will be recorded. Screen Failures are not considered evaluable.

Screen Failures may be identified through review of medical history, assessments, measures, laboratory results, or conversations with the participant. Medical assessments may be repeated for confirmation. At any time during Screening, if a potential participant is deemed to be ineligible, classify as a Screen Failure, notify the potential participant that they are unfortunately not eligible for the study, and do not schedule additional Screening assessments. Participants who fail

Screening may be rescreened at a later date if deemed appropriate by the investigator but should sign a new copy of the Informed Consent Form (ICF). Screen Failures may request a referral to an outside therapist if needed. Screen Failures that were scheduled for an IR assessment will be entered into the Electronic Data Capture (EDC) system.

5.3.3 Pre-Randomization Early Terminations

‘Pre-randomization Early Terminations’ are defined as participants who were deemed eligible and enrolled in the study at Visit 0, but are deemed ineligible prior to the first Experimental Session and do not have enrollment confirmed at Visit 4. These participants may fail to meet all Inclusion Criteria and may meet one or more Exclusion Criteria or withdraw consent prior to Enrollment Confirmation or the site may withdraw the participant for reasons described in [Section 5.3.4 Early Termination from the Study](#). Participants who fail Enrollment Confirmation may not be re-enrolled into this study at a later date. All enrolled participants, even those failing Enrollment Confirmation, will be maintained in the EDC system. Pre-randomization Early Terminations are not considered evaluable.

Pre-randomization Early Terminations may be identified through review of medical history, assessments, measures, laboratory results, or conversations with the participant. At any time during the Preparatory Period, if a potential participant is deemed to be ineligible, classify as a Pre-randomization Early Termination, notify the potential participant that they are unfortunately not eligible for the study, and do not schedule additional assessments. Do not randomize the participant. Pre-randomization Early Terminations will be provided an Exit Plan as described in [Section 8.4.3.2 Exit Plan](#).

5.3.4 Early Termination from the Study

Participants who are removed from the study after they are randomized and receive IMP but do not complete the study may fall into one of these categories: Post-randomization Early Termination or Dropout. If the participant has received IMP in at least one Experimental Session and completed one CAPS-5 assessment beyond Baseline, they will be considered evaluable. All participants who receive IMP in at least one Experimental Session will be included in all safety analyses.

Participants can withdraw from treatment or withdraw consent at any time for any reason without judgment. The site team can withdraw a participant if, in their clinical judgment, it is in the best interest of the participant or if the participant cannot comply with elements of the protocol that are critical for safety or for the scientific integrity of the study. If the site team makes the decision to terminate the participant from treatment or the study, they will explain the reason for withdrawal and document in the participant’s source records and Electronic Case Report Form (eCRF). If a participant develops any Exclusion Criteria that, in the opinion of the Medical Monitor or Site, affects the safety of the participant, including psychiatric diagnosis, medical diagnosis, pregnancy, or requiring use of prohibited medications, the participant will discontinue treatment in Experimental Sessions but remain in the study for the associated Integrative Sessions. Participants whose Experimental Sessions are delayed by the COVID-19 pandemic may start any of these medications during the delay, as clinically indicated. When study visits resume, they will be given the option to resume Experimental Sessions after tapering off of these medications per [Section 12.1 Tapering Instructions](#). Any time a participant terminates from the study early, the site team will attempt to obtain information about AE outcomes if appropriate, as determined by the site physician and Medical Monitor. The site team will provide the participant with an Exit Plan as described in [Section 8.4.3.2 Exit Plan](#).

Data will be collected from participants who terminate early as follows:

- **Post-randomization Early Termination:** Participants who discontinue study treatment but continue to participate in Independent Rater primary and secondary outcome assessments. Data collection by IRs will continue on the same schedule as planned through Study Termination visit procedures.
- **Dropout:** If a participant decides to withdraw consent completely, they will terminate without further follow-up. If the participant agrees, they will complete a final CAPS-5 assessment. These participants are defined as dropouts who withdraw consent due to any reason after receiving at least one dose of IMP and no longer participate in the study (i.e., no further contact with investigators or site staff). Data collected on study participants up to the time of withdrawal of consent will remain in the trial database in order to maintain scientific validity. Removal of data from the database would undermine the scientific and ethical integrity of the research.

5.3.5 Lost to Follow-up

A participant will be considered lost to follow-up if they fail to attend scheduled visits and are unable to be contacted by the site staff. If the participant has completed at least one Experimental Session and one CAPS-5 assessment beyond Baseline, they will be considered evaluable. All participants with at least one Experimental Session will be included in the safety analysis.

If a participant does not attend a scheduled visit, the site must attempt to contact the participant to reschedule the visit as soon as possible and emphasize the importance of complying with the protocol specified visit schedule. The staff should determine if the participant is willing to comply with future visits.

If a participant does not respond to this initial contact, the site staff must make multiple efforts to contact the study participant and document each attempt in the source record. At least three attempts should be made via telephone, over the course of approximately 7 days, with calls at different times of day. If telephone contact fails, an email should be sent if such contact information was provided. The emergency contact the participant provided should be contacted and asked to attempt contact with the participant. Lastly, a certified letter (or equivalent) should be sent to their last known mailing address. If the participant fails to respond to all of these contacts, they will be considered to have withdrawn from the study and are lost to follow-up.

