- On the day of the Experimental Session, the participant will arrive approximately 30 to 60 minutes prior to IMP administration.
- The site team will ensure the participant has not used caffeine or nicotine 2 hours prior and has fasted for 10 hours prior to IMP administration and complied with all other requirements per [Section 4.3 Lifestyle Modifications](#).
- The site team will inquire about any possible changes in health to ensure the participant continues to meet all eligibility requirements and record AEs as described in [Section 11.0 Safety](#).

- The site team will instruct the participant that they will not be able to use caffeine or nicotine at least 6 hours after the IMP administration.
- The site team will complete urine drug screen, pregnancy test, and concomitant medication review.
 - A positive drug screen will be reviewed by the site physician and may be cause for delaying IMP administration to a later time, rescheduling the session to a later date, or withdrawing the participant from the study, based on Medical Monitor review.
 - A positive pregnancy screen is cause for withdrawal from the protocol.
- The therapy team will administer Since Last Visit C-SSRS.
- The therapy team will review procedures for the Experimental Session with the participant and discuss the participant's goals, intentions, and concerns and some of the commonly experienced effects of MDMA. The choice of whether to keep the dose the same or change it from the first Experimental Session will be made by the therapy team in consultation with the site physician based on observed response, tolerability to the previously administered dose, and discussion with the participant.
- If the participant continues to be eligible, the session will proceed.
- Baseline blood pressure, body temperature, and pulse will be measured just prior to administration of the initial dose.

During the Experimental Session

- After video recording has begun, at approximately 10:00 in the morning, a qualified staff member will administer the initial dose of IMP with an electrolyte-containing fluid. The participant will sit or recline on comfortable furnishings. Eyeshades and a program of music will be provided for the participant if they wish to use them. Whenever they wish, participants may speak to the therapy team, who will provide guidance and support, as needed.

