To ensure that all participants regardless of group assignment are treated in a similar manner, the sites will be required to follow the protocol and Treatment Manual delineating minimum length of time per visit type and describing delivery of treatment. All Experimental Sessions are required to be at least 8 hours long. Adherence to the Treatment Manual will be randomly checked by review of video by blinded Adherence Raters. The sponsor will monitor data in real-time to ensure complete data collection for all participants, including those who discontinue treatment. Sites will be required to make and document a specific number of attempts to obtain follow-up data per protocol. All randomized participants who receive at least one dose of IMP and complete at least one follow-up assessment will be included in the final mITT primary efficacy analysis.

The DMC will act in an advisory capacity to the sponsor to monitor participant safety, data quality, and review Phase 3 outcomes to ensure the trial is conducted safely, ethically, and meets endpoint objectives. The DMC will be the only group reviewing group-unblinded interim data. The DMC will not be able to recommend early Study Termination for efficacy at the interim analysis, which will be conducted after N=100 have been enrolled. A single representative within MAPS will be designated to receive written communication of recommendations following the interim DMC review of the trial. This communication will be limited to the results needed for the decision of sample size re-estimation. The sponsor representative within MAPS and DMC members will sign a written confidentiality agreement in order that the precise rules governing sample size re-estimation may not be disclosed to the outside community. No other adaptions to the study design will be made based on this interim analysis. The sponsor representative from MAPS will not be part of any trial decisions or administration after the sample size re-estimation has been communicated to MPBC who will continue to be the trial organizer.

If there is an emergency requiring knowledge of a participant's condition assignment, the blind may be broken for an individual participant through the IWRS. Upon database lock, the study will be unblinded and participants will be notified of treatment assignment.

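### Protocol 5.3.5 treats an unreachable participant as withdrawn after one round of contact attempts and requires no new attempt when a later CAPS-5 assessment, including Visit 19, falls due

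*Protocol*

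**What the plan says.** **Unreachable participants.** Protocol 5.3.5 begins with a missed scheduled visit and a first attempt to reschedule. If that fails: "At least three attempts should be made via telephone, over the course of approximately 7 days". An email and the emergency contact follow, and then: "Lastly, a certified letter (or equivalent) should be sent to their last known mailing address". The condition for closing the record is "If the participant fails to respond to all of these contacts", and the stated consequence for such participants is that "they will be considered to have withdrawn from the study and are lost to follow-up". No waiting time is given after the telephone stage, and the section does not mention the CAPS-5 assessments still to come.

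**Site-initiated removal.** Protocol 5.3.4 says: "The site team can withdraw a participant if, in their clinical judgment, it is in the best interest of the participant". It also allows withdrawal of a participant who cannot comply with critical parts of the protocol. Its scope goes beyond treatment: "If the site team makes the decision to terminate the participant from treatment or the study". After a positive drug screen, 8.3.1 lists among its options "withdrawing the participant from the study, based on Medical Monitor review". Section 5.3.4 then gives two data-collection categories. Post-randomization Early Termination covers those who stop treatment and stay in the independent rater (IR) assessments. Dropout covers those who withdraw consent.

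**What the rest of the plan relies on.** Protocol 9.4 commits the sponsor to real-time monitoring "to ensure complete data collection for all participants, including those who discontinue treatment". SAP 8.2 continues IR collection after early termination in order to keep missing data down. SAP 8.7.2 argues that the de facto analysis can be regarded as having no missing data, because collection continues for everyone.

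**The concern.** Visit 19 is a telemedicine interview, so someone who has stopped attending the site could still provide the primary outcome. A rule that closes the record after one unanswered round of contacts, weeks or months before that interview is due, gives up scores that might have been retrieved. Silence is also recorded as withdrawal, although the participant has not withdrawn consent.

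Participants who fall silent may do so because of how they are responding, and that kind of missingness cannot be undone at analysis. Few losses are planned for, so each one counts. The site-removal wording raises a related question: a consenting participant whom the site ends from the study has no clear outcome-collection rule.

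**Working it through.** **1. Timing inputs (Protocol 8.3.1, 8.3.3, 8.4.2).** V5 = V3 + 4 to 7 days; V6 = V5 + 1; V17 = V15 + 3 to 14; V18 = V15 + 21 to 35; V19 = V3 + 105 to 147 and V15 + 42 to 70. Closure is taken as the missed-visit day + 7. This is an assumption and the shortest reading, since the letter stage has no stated wait. A longer wait shortens every interval below.

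| Missed visit | Closed at | Time left before V19 window ends |
|---|---|---|
| V6 | V3 + 12 to 15 | 147 − 15 = 132 to 147 − 12 = 135 days (18.9 to 19.3 weeks) |
| V17 | V15 + 10 to 21 | 70 − 21 = 49 to 70 − 10 = 60 days (7.0 to 8.6 weeks) |
| V18 | V15 + 28 to 42 | 70 − 42 = 28 to 70 − 28 = 42 days (4.0 to 6.0 weeks) |
| V19 | V3 + 112 at the earliest | 147 − 112 = 35 days (5.0 weeks), down to none |

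Counted from V15, the V19 window opens at day 42. A V17 miss is therefore closed 42 − 21 = 21 to 42 − 10 = 32 days before it opens, and a V18 miss 42 − 42 = 0 to 42 − 28 = 14 days before. A participant who received all three sessions can be closed out before the primary assessment could have been attempted.

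**2. Which analysis loses the score.** Protocol 14.2.1.1 and SAP 8.7.1 exclude CAPS-5 data collected after treatment discontinuation from the primary de jure analysis. For someone lost before Session 3 who does not resume, a recovered V19 score serves the de facto analysis, which SAP 8.7.2 calls exploratory and supportive. The primary score is lost directly only after V15.

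**3. The plan's power figure.** Inputs (Protocol 14.1): difference 37.4 − 20.5 = 16.9; variance 335 + 280 = 615, SD 24.8; 47 per group; two-sided alpha 0.0499. A two-sample calculation gives 16.9 / (24.8 × √(2/47)) = 3.30, and 3.30 − 1.96 = 1.34, so power is 91.0% (90.5% with the t distribution), against the stated 90%. With five further losses per group (n = 42) it is 87.7%.

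**4. Bias per lost participant.** Assume one of 50 MDMA participants is lost after Session 3 and would have scored at the placebo mean. With the SAP section 7.0 conversion, the planned difference is 16.9 × 20/34 = 9.94 CAPS-5 points.

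- *Upper end, earlier visits ignored:* 9.94 / 50 = 0.20 points.
- *Allowing for the mixed model's use of V8 and V13:* assume the participant followed the placebo trajectory, so was 17.2 − 5.5 = 11.7 and 31.1 − 12.8 = 18.3 points below the MDMA mean change, 30.0 in total. With variance 615 and a common covariance c, each earlier deviation has weight c / (615 + c).
  - c = 335: 335/950 × 30.0 = 10.6 of the 16.9-point shortfall is predicted. Remainder 6.3 × 20/34 / 50 = 0.07.
  - c = 335 + 0.5 × 280 = 475: 475/1090 × 30.0 = 13.1 is predicted. Remainder 3.8 × 20/34 / 50 = 0.05.

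The range is about 0.05 to 0.20 CAPS-5 points per such participant, against a planned 9.94.

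**5. Site removal, side by side.** Early Termination in 5.3.4 keeps IR assessments for those who discontinue treatment. Dropout requires withdrawn consent. The final CAPS-5 in 8.4.2 is for those who have withdrawn from treatment. None of these expressly covers a consenting participant whom the site removes from the study.

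**The case against.** The protocol does more than make three calls. Withdrawal is declared only after every contact step has failed. Section 8.3.2 schedules calls to Day 14 after each session, 8.0 asks sites to consider extra calls after gaps of more than 7 days, and inclusion criterion 5 requires a contact person. Section 9.4 requires a documented number of follow-up attempts, and nothing forbids later contact or turns away a participant who returns. All of this stands, but none of it sets an attempt at the V13 or V19 window.

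Several stronger readings are tempting and are not supported:

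- *A week of silence ends participation.* Seven days is the telephone stage only.
- *Any missed visit forfeits 7 to 19 weeks.* That range fits V6 to V17, not V18 or V19, and site removal has no fixed timing.
- *Each loss shifts the primary result by 0.2 points.* That ignores the mixed model's use of earlier visits. SAP Table 5 also plans Jump to Reference for MDMA participants who leave the study without further data, which closely matches this scenario. The table has no lost-to-follow-up row, however, so a silent participant would enter it only by being labelled withdrawn.
- *Sites will remove participants differently by arm.* Nothing in the documents shows this. Study withdrawal in 8.3.1 is one of three options and depends on Medical Monitor review.
- *Site removal always ends outcome collection.* Most specific triggers (exclusion criteria in 5.3.4, antidepressants in 12.3) stop treatment and keep follow-up. Section 5.3.4 can also be read as placing every removed participant in one of its two categories.

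Finally, barring site-initiated study withdrawal would reach into participant management, since 10.1.2 notes that outcome interviews can themselves cause distress. That objection is accepted.

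**Conclusion.** The point holds in limited form. Section 5.3.5 equates silence with withdrawal and sets no re-contact at later CAPS-5 windows, which sits badly with the aims of Protocol 9.4 and SAP 8.2 and with the no-missing-data argument in SAP 8.7.2. The retrievable time is real, but every interval above is a maximum that rests on 7-day closure.

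The effect on the primary result is likely to be small. It requires losses after Session 3, and the bias figures rest on an assumed placebo-level outcome and an assumed covariance. How many such losses would occur, and how many could be recovered, cannot be derived from the documents: SAP 8.2 expects up to 5% early termination and Phase 2 had 7.5% dropout, both from all causes. The power cost is modest. This is a worthwhile and cheap improvement, not a threat to the trial's conclusion. On site removal, the documents leave a gap to be reconciled and do not show a demonstrated loss of data.

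**What to change.** **Protocol 5.3.5.** Keep unreachable participants who have not withdrawn consent in the study. Repeat the contact attempts at each remaining CAPS-5 window. Assign lost-to-follow-up status only when the Visit 19 window has closed without contact: 147 days after V3, or 70 days after V15 when sessions were delayed.

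**Protocol 5.3.4 and 8.3.1.** Reconcile the references to ending study participation with Protocol 9.4 and SAP 8.2 and 8.7.2, so that the documents state whether IR outcome assessments continue through Visit 19 for a site-removed participant who has not withdrawn consent. This concerns outcome collection only and leaves the site's discretion over participant management unchanged.

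The cost is protocol wording and a few extra contact attempts for a small number of participants, with no added visits or sample size.
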